Study Title: A randomized, double-blinded, placebo-control trial of IV ondansetron to prevent pruritus in children who receive intrathecal morphine.
Study Phase: 4
Primary Objective: Demonstrate efficacy of Ondansetron (Zofran) to reduce incidence and intensity of pruritus as a side effect of IntraThecal Morphine (ITM)
Study Design: Prospective, randomized, double-blind, placebo controlled
Study Population: ages 3-17 inclusive
Diagnosis and Main Criteria for Inclusion Each subject must meet the following criteria to be enrolled in this study: Scheduled for any procedure necessitating ITM for pain management. Wt <= 100kg Ability to use verbal or pictorial scoring scales Parental informed consent Subject informed assent, as applicable Subjects who meet any of the following criteria will be excluded from study: Inability to use verbal or pictorial scoring scales (developmental delay) Hypersensitivity to selective 5-HT ₃ receptor antagonists Diagnosed congenital long QT syndrome Severe hepatic impairment Pregnancy and nursing mothers Use of serotonin specific reuptake inhibitors within 14 days Use of serotonergic-nonadrenergic reuptake inhibitors within 14 days Current use of any medications that prolong QT interval
Test Product; Dose; and Mode of Administration: Intervention group: This arm will receive (in a blinded fashion) 0.1 mg/kg of Ondansetron IV diluted in normal saline to a volume of 5 mLs intra-operatively and Ondansetron IV 0.1 mg/kg diluted in normal saline to a volume of 5 mLs every 6 hours for 24 hours postoperatively (not to exceed 40 mg in 24 hours).

Reference or Placebo Therapy; Dose; and Mode of Administration:

Control group:

This arm will receive (in a blinded fashion) a volume-matched placebo (normal saline) intraoperatively as well as IV every 6hrs for 24 hours postoperatively.

Duration of Treatment: Intraoperative time period plus 24 hours from end of surgery.

Statistical Methods:

Data will be summarized using descriptive methods. Parametric data will be analyzed between groups using unpaired t tests or Mann Whitney U, as appropriate. Rankings of pruritus and PONV will be coded as none-mild vs. severe and Chi-squared and Fishers' Exact tests will be used to compare these outcomes between groups. Significance will be accepted at the 5% level.

1 INTRODUCTION

1.1 Indication

Pruritus is one of the most common and bothersome side effects of intrathecal morphine (ITM) in children, with a reported incidence of 30-70% (1, 2, 13, and 15). We previously found a 40% incidence of pruritus in young children who received intrathecal morphine for major urologic surgery (2) (retrospective review, n= 77, anti-pruritic treatment required in 31 cases). Clinicians, who have witnessed unbearable itching and scratching in their young patients after intrathecal morphine, may be reluctant to offer this effective pain control to future patients, for fear of these unpleasant sequelae.

1.2 Background and Rationale

The mechanism of morphine-induced itch is not fully elucidated. (1, 16, 19). However, neuraxial opioids induce more frequent and intense itch than peripherally administered doses (26). Centrally located Mu-opioid receptors, in the medullary dorsal horn, may play a role, and activation of this site with an opioid injection induced a dose related scratch frequency in primates (23). The mu opioid receptors, but not other opioid receptor subtypes, appear to mediate the neuraxial opioid-induced itch as opposed to intravenously administered opioids (21, 22, 25). However, the physiology is more complex, as morphine induced pruritus is not always reversed with naloxone (13) and effective treatments for neuraxial induced pruritus include partial opioid agonists (1, 13), 5HT3 antagonists (4-7), propofol (13, 24), and prostaglandin modulation (19).

1.3 Hypothesis

Pre-emptive and continued blocking of 5HT3 receptors with the 5HT3 receptor antagonist ondansetron, given intravenously prior to ITM and 6 hourly thereafter, will reduce the incidence and intensity of pruritus as a side effect of morphine, in our pediatric patients.

Secondary outcomes to be studied: Post-operative nausea and vomiting and any adverse events.

1.4 Previous Human Experience

5HT3 antagonists are considered among the first line of treatments for morphine-induced nausea as well as pruritus in adult, particularly obstetric, populations (4, 7, 8, 19). A review of placebo RCTs, using prophylactic 5HT3 antagonists for pruritus in neuraxial opioids, found NNTT = 7 to reduce pruritus in adults (29). 5HT3 antagonists block the effects of morphine in animal studies (3). There is a high density of 5HT3 receptors in the nucleus of the facial and trigeminal nerve (20, 25). An “itch center” has been proposed at the spinal tract nucleus of the trigeminal nerve (18). More specifically, pre-emptive (27, 28) and around-the-clock ondansetron (28) dosing with ondansetron has been shown to reduce itch (both incidence and intensity), in adults who received intrathecal opioids.

In the pediatric population, case reports (9-11) suggest ondansetron is an effective treatment for pruritus, but to date there are no data to support the efficacy of 5HT3 antagonists in preventing or treating ITM-related pruritus in children.

In contrast, antihistamines such as diphenhydramine, while used in many pediatric settings, have been shown to be ineffective on opioid-related pruritus, in recent reviews (1, 13). This is corroborated by research in primates (23).

2 STUDY OBJECTIVES AND ENDPOINTS

2.1 Objectives

- Incidence and severity of pruritus in both study groups
- Incidence and severity of nausea and vomiting in both study groups

2.2 Endpoints

2.2.1 *Primary Endpoint*

Incidence and severity of pruritus within 24 hours post-operatively

2.2.2 *Secondary Endpoint*

- Post-operative nausea and vomiting within 24 hours post-operatively
- Adverse events intra-operatively and within 24 hours post-operatively

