6.2 Treatment Study Period

6.2.1 *Day of Surgery through 24 hours post-operative*

Preoperatively, the medical history will be reviewed to confirm that no exclusion criteria have developed since informed consent.

In the operating room, the subject will receive an intra-operative bolus dose of study drug labeled “antipruritic study drug” (ondansetron, 0.1mg/kg or placebo) IV, prior to intrathecal

morphine injection, followed by around-the-clock study drug labeled “antipruritic study drug” (ondansetron doses, of 0.1mg/kg or placebo) IV every 6 hours for 24 hours from OR end time.

Subjects in the operating room, recovery room, and PACU will be monitored as per standard clinical care.

Data collection

For the first 24 hours after surgery, subjects will be visited in the Post Anesthesia Care Unit (PACU), the evening of surgery, the next morning and at 24 hours postoperatively (not between the hours of 10p-7a) to obtain the presence and degree of adverse effects, our primary outcomes. Pruritus will be scored similar to previous pediatric studies, as 0 = none; 1 = mild/tolerable/not requiring treatment; 2 = severe/intolerable/requiring treatment (12). We will use a similar method to quantify the amount of nausea/vomiting each patient experiences (0 = no nausea/vomiting; 1 = mild/tolerable nausea/vomiting not requiring treatment; 2 = severe/intolerable nausea/vomiting requiring treatment) (14). The following data will also be collected: all analgesics, antiemetic, and antipruritic agents used.

SCHEDULE OF ACTIVITIES

Protocol Activity	Screen	Day of surgery	Follow-up: OR end +24 hrs
Informed Consent	X		
Review of medical history	X	X	
Vitals	X	X	
Randomization		X	
Treatment with study agent		X	X
Pruritus and PONV assessment			X
Adverse Event Assessment		X	X
Concomitant Medication	X	X	X

Note: Pregnancy test is performed as standard of care for all post-menarcheal females scheduled for surgery at C. Mott Children's Hospital.

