7 ASSESSMENTS

7.1 Primary Endpoint Assessments

For the first 24 hours, subjects will be visited in the PACU, the evening of surgery, the next morning and at 24+/-3 hours (not between the hours of 10p-7a) to obtain the presence and degree of adverse effects, our primary outcomes. Pruritus will be scored similar to previous pediatric studies, as 0 = none; 1 = mild/tolerable/not requiring treatment; 2 = severe/intolerable/requiring treatment (12).

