All AEs will be recorded by the Investigator from the time the subject signs informed consent until hospital discharge. AEs and serious adverse events (SAEs) will be recorded in the subject's source documents. All SAEs must be reported to the IRB according to the University of Michigan IRB reporting requirements.

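### The adverse-event endpoint spans the same 24 hours as study-drug dosing, so it covers only 0 to 6 hours after the last dose, although Section 8 already records events to discharge

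*Combined protocol and SAP*

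**What the plan says.** Section 2.2.2 gives the second of two secondary endpoints as "Adverse events intra-operatively and within 24 hours post-operatively". The study summary at the front of the protocol gives the duration of treatment as "Intraoperative time period plus 24 hours from end of surgery", and Section 6.2.1 has the post-operative study drug given "IV every 6 hours for 24 hours from OR end time".

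Section 8 uses a wider period for recording: "All AEs will be recorded by the Investigator from the time the subject signs informed consent until hospital discharge". Under Section 3, consent may be taken in clinic, before the day of surgery.

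In the Schedule of Activities (Section 6.2.1), the row "Adverse Event Assessment" is marked under the day of surgery and under "Follow-up: OR end +24 hrs". It has no mark at screening, and there is no later column. Section 7.1 sets the final bedside visit at "24+/-3 hours (not between the hours of 10p-7a".

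Section 3 says the groups will be compared over the 24 hours after surgery. Section 9.2 names tests for pruritus and nausea/vomiting rankings but says nothing specific about adverse events.

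**The concern.** A safety endpoint normally runs some way beyond the last exposure, so that events following the final dose are counted. Here the endpoint and the treatment period end together. An event that starts after 24 hours should be written down under Section 8, yet it does not enter the endpoint, and no section says it will be shown by arm.

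The protocol treats drug-related risk as real: Section 4.1.2 excludes children with congenital long QT syndrome, QT-prolonging medication or severe hepatic impairment. A report that followed Section 2.2.2 literally could give a by-arm safety count that omits events following a dose at 24 hours, even though the data were in hand.

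**Working it through.** The plan states no figure on this point to reproduce. The check is on timing.

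**Inputs**
- Endpoint closes at 24 h after surgery (Section 2.2.2).
- Post-operative dosing every 6 h for 24 h from the end of surgery (Section 6.2.1). The time of the last dose is not stated.
- Final visit at 24 ± 3 h (Section 7.1), that is, from 24 − 3 = 21 h to 24 + 3 = 27 h.

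**Formulas**, with t the time of the last dose in hours after the end of surgery
- Endpoint cover after the last dose = 24 − t.
- Final visit relative to the last dose = from 21 − t to 27 − t.

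| Reading of the dosing schedule | t | Endpoint cover | Final visit relative to last dose |
|---|---|---|---|
| Doses at 0, 6, 12, 18 h | 18 | 6 h | 3 h after to 9 h after |
| Doses at 6, 12, 18, 24 h | 24 | 0 h | 3 h before to 3 h after |
| Every 6 h from an intra-operative dose 2 h before end of surgery (assumed): 4, 10, 16, 22 h | 22 | 2 h | 1 h before to 5 h after |
| The same, 4 h before (assumed): 2, 8, 14, 20 h | 20 | 4 h | 1 h after to 7 h after |
| The same, 6 h before (assumed): 0, 6, 12, 18, 24 h | 24 | 0 h | 3 h before to 3 h after |

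Under every reading the cover is between 0 and 6 h, at most one dosing interval. In the second row, one of the five doses (one intra-operative, four post-operative) has no endpoint follow-up.

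**Effect of the night-time bar on visits.** If surgery ends at clock time T, the visit window is T − 3 h to T + 3 h on the following day. For T between 10 pm and 1 am, the part of that window outside 10 pm to 7 am lies wholly before 24 h. For T after 4 am and before 7 am, the permitted part lies after 24 h. The protocol does not say how often surgery ends at such times.

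**The windows side by side**
- Endpoint (2.2.2): intra-operative period to 24 h.
- Recording (Section 8): consent to discharge.
- Scheduled assessment (6.2.1): day of surgery and 24 h after the end of surgery.

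For a child still in hospital at 24 h, the endpoint window lies inside the recording window. Two stretches are recorded but outside the endpoint: consent to the intra-operative period, and 24 h to discharge. Neither has a mark in the adverse-event row of the Schedule.

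**The case against.** The strongest reply is that nothing here is inconsistent. A recording period wider than an endpoint window is ordinary practice. A reader might infer that the safety comparison depends on which window the analyst picks. The documents do not support that: Section 2.2.2 fixes the endpoint window, Section 3 sets the group comparison over the 24 post-operative hours, and Section 8 says when events are recorded, not which are compared. This part of the reply stands.

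A fixed 24-hour window also gives every child the same follow-up. Follow-up to discharge varies, and length of stay could itself be affected by treatment through pruritus or vomiting. That stands too, and is the reason to keep the 24-hour count.

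The final visit may be as late as 27 h, its window is stated under the primary endpoint, and recording under Section 8 continues to discharge. A visit at 21 h therefore does not close adverse-event capture. Nor would including events before the first syringe bias the comparison: randomization should balance them. They would add noise and pull a ratio towards one, but need not move an absolute difference.

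The reply leaves one gap. Events after 24 h are to be collected, but no section says they will be reported by arm. Section 9.2 does not fill it, since it specifies no adverse-event analysis at all.

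**Conclusion.** The point holds as a modest, inexpensive improvement. The endpoint gives 0 to 6 h of cover after the last dose, depending on whether that dose falls at 24 h or 18 h, and excludes later events that Section 8 already requires to be recorded.

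Two stronger inferences are not supported. A reader might conclude that events after 24 h are lost. They are not: they are left out of the endpoint, but recording runs to discharge, and Section 11.3.1 has the study team review all serious events. A reader might also conclude that the endpoint misses everything after the final dose. That is so only if the last dose is at 24 h; with a last dose at 18 h, the first 6 h after it are counted.

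The size is known only in hours. With no adverse-event rates and no lengths of stay in the documents, neither the number of events excluded nor any effect on the comparison between arms can be computed. The conclusion rests on reading Section 2.2.2 literally and on the children still being in hospital after 24 h.

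**What to change.** 1. In Section 2.2.2, keep the intra-operative-to-24-hour count, which gives equal follow-up. Add a by-arm tabulation of adverse events that start or worsen from the first study syringe to hospital discharge.
2. List events between consent and the first syringe separately.
3. Align the Schedule of Activities with Section 8, so that the final adverse-event check follows the last study dose. Chart review is enough, including when that time falls in the hours barred to visits.
4. Name both tabulations in Section 9.2 and show them side by side.

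Cost: wording in three sections, and no data collection beyond chart review. Dosing is unchanged. The drawback is that follow-up to discharge differs between children, so that count should be read next to the fixed-window one and not in place of it.

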3 STUDY DESIGN

After obtaining IRB approval and informed consent, we will recruit children ages 3-17 years (able to use verbal or pictorial scoring scales) who are scheduled to intrathecal morphine for a surgical procedure and weigh less than or equal to 100kg.

We will recruit 130 children, and randomize using a random numbers table, stratifying for female gender. The patients who have consented to take part in the study, their families and caregivers, their medical team and the trained observers will be blinded to the treatment being given.

Our proposed ondansetron regime comprises an intra-operative bolus dose of ondansetron, 0.1mg/kg IV, prior to intrathecal morphine injection, followed by around-the-clock ondansetron doses, of 0.1mg/kg IV every 6 hours. We will compare this to a standardized control regime comprising an intra-operative bolus dose of saline placebo and around the clock placebo for 24 hours. 56 patients will comprise each group. All children in both groups will be cared for using a standard, current practice, which includes intra-operative anti-emetics per our departmental algorithm for PONV (Postoperative nausea and vomiting), described below.

Rescue orders for pruritus and PONV are also summarized below. See the attached protocol flowsheet for an overview. Naloxone is routinely ordered, to be given as needed for the treatment of respiratory depression or over-sedation only. We will compare our study group with the control group over the 24 postoperative hours with blinded observers / interviewers.

STANDARD OF CARE FOR PONV PREVENTION

As per standard of care, all subjects will receive dexamethasone and diphenhydramine intra-operatively for PONV prevention. For patients who fall into the “High Risk for PONV” category (according to departmental standard of care algorithm), anesthesiologist may, at their discretion, consider any of the following: pre-operatively aprepitant; fluid bolus 30ml/kg; Total Intravenous Anesthesia (TIVA); Sub-hypnotic dose propofol of 1mg/kg infused at 20mcg/kg/min.

STUDY PROCEDURES Pre-Operatively, Intra-Operatively and Post-Operatively:

- **Pre-op:** Patients will be consented in clinic whenever possible or on the day of surgery and randomized, with gender stratification. Patients, their families and health care professionals will be blinded as to whether the patient is in the treatment or control group.
- **Intra-op:** Induction of general anesthesia per standard of care. Syringe of drug labeled “Anti pruritic study drug” to be given IV, prior to intrathecal morphine administration, by anesthesiologist in the OR:
 - Study group: Syringe contains ondansetron 0.1mg/kg, diluted to a volume of 5 mls (not to exceed 5 mg/dose).

- Control group: Syringe contains normal saline, 5 mls.
- **Post-op:** Syringe of drug labeled “Anti pruritic study drug” to be given IV, q6h for 24 hours by RN on the floor:
 - Study group: Syringe contains ondansetron 0.1mg/kg, diluted to a volume of 5 mls (not to exceed 40 mg in 24 hours or 10 mg/dose).
 - Control group: Syringe contains normal saline, 5 mls.

STANDARD OF CARE FOR POST-OPERATIVE RESCUE TREATMENT OF PRURITUS AND PONV

Regardless of study group, all subjects will receive standard of care treatment for pruritus and or PONV should it be required at any time post-operatively.

Standard of Care rescue medications for pruritus:

- First line: PRN nalbuphine.
- Second line PRN diphenhydramine.

Standard of care rescue medication for PONV:

- First line: PRN prochlorperazine.
- Second line: promethazine

4 SUBJECT SELECTION

4.1 Subject Recruitment

4.1.1 *Inclusion Criteria*

1. Age: 3-17 years, inclusive and wt </= 100kg
2. Scheduled for any procedure necessitating ITM
3. Ability to use verbal or pictorial pain assessment tools and techniques
4. Informed consent and assent (if applicable)

4.1.2 *Exclusion Criteria*

1. Inability to use verbal or pictorial scoring scales
2. Hypersensitivity to selective 5-HT₃ receptor antagonists

3. Diagnosed congenital long QT syndrome
4. Current use of any medications that prolong QT interval
5. Severe hepatic impairment
6. Pregnancy or nursing mothers
7. Use of serotonin specific reuptake inhibitors within 14 days
8. Use of serotonergic-noradrenergic reuptake inhibitors within 14 days

5 STUDY TREATMENTS

5.1 Allocation to Treatment

Subjects will be randomized via previously generated random numbers table and stratifying for female gender.

5.2 Breaking the Blind

The randomization can be broken, if necessary per the physicians caring for the subject to ensure subject safety. In the case of such a medical emergency, the blind will be broken by the study pharmacist or pharmacy designee.

5.3 Drug Supplies

5.3.1 *Formulation, Preparation and Dispensing*

All study drugs for this study are available on formulary. The study pharmacist will have access to the random numbers table denoting group assignment and will prepare the blinded study drug for each patient and deliver it the appropriate operating room on the day of surgery.

5.3.2 *Drug Storage and Drug Accountability*

All study medications are stored in accordance with Mott OR Pharmacy standards. Drug accountability will be maintained by the study pharmacist and designated and trained Mott OR Pharmacy staff.

6 STUDY PROCEDURES

6.1 Screening

Subjects will be identified 2 ways:

1. Review of the applicable clinic schedules
2. Review of the daily Operating Rooms schedule

6.2 Treatment Study Period

6.2.1 *Day of Surgery through 24 hours post-operative*

Preoperatively, the medical history will be reviewed to confirm that no exclusion criteria have developed since informed consent.

In the operating room, the subject will receive an intra-operative bolus dose of study drug labeled “antipruritic study drug” (ondansetron, 0.1mg/kg or placebo) IV, prior to intrathecal

morphine injection, followed by around-the-clock study drug labeled “antipruritic study drug” (ondansetron doses, of 0.1mg/kg or placebo) IV every 6 hours for 24 hours from OR end time.

Subjects in the operating room, recovery room, and PACU will be monitored as per standard clinical care.

Data collection

For the first 24 hours after surgery, subjects will be visited in the Post Anesthesia Care Unit (PACU), the evening of surgery, the next morning and at 24 hours postoperatively (not between the hours of 10p-7a) to obtain the presence and degree of adverse effects, our primary outcomes. Pruritus will be scored similar to previous pediatric studies, as 0 = none; 1 = mild/tolerable/not requiring treatment; 2 = severe/intolerable/requiring treatment (12). We will use a similar method to quantify the amount of nausea/vomiting each patient experiences (0 = no nausea/vomiting; 1 = mild/tolerable nausea/vomiting not requiring treatment; 2 = severe/intolerable nausea/vomiting requiring treatment) (14). The following data will also be collected: all analgesics, antiemetic, and antipruritic agents used.

SCHEDULE OF ACTIVITIES

Protocol Activity	Screen	Day of surgery	Follow-up: OR end +24 hrs
Informed Consent	X		
Review of medical history	X	X	
Vitals	X	X	
Randomization		X	
Treatment with study agent		X	X
Pruritus and PONV assessment			X
Adverse Event Assessment		X	X
Concomitant Medication	X	X	X

Note: Pregnancy test is performed as standard of care for all post-menarcheal females scheduled for surgery at C. Mott Children's Hospital.

7 ASSESSMENTS

7.1 Primary Endpoint Assessments

For the first 24 hours, subjects will be visited in the PACU, the evening of surgery, the next morning and at 24+/-3 hours (not between the hours of 10p-7a) to obtain the presence and degree of adverse effects, our primary outcomes. Pruritus will be scored similar to previous pediatric studies, as 0 = none; 1 = mild/tolerable/not requiring treatment; 2 = severe/intolerable/requiring treatment (12).

